6.3.3. FACIT-Fatigue

The FACIT-Fatigue questionnaire consists of 13 items scored on a 5-point Likert scale (0 = not at all, 4 = very much). The FACIT-Fatigue subscale scoring guideline (version 4) will be used as follows (https://www.facit.org/measures/FACIT-Fatigue):

- All negatively stated items (ie, all items except An5 and An7 from the eCRF) are to be reversed by subtracting the response from 4.
- After reversing the proper items, all items are summed to obtain a score.

• The Fatigue subscale score is then calculated by multiplying the sum of the item scores by 13, then dividing by the number of items answered.

When there are missing data, prorating by subscale in this way is acceptable as long as more than 50% of the items were answered. The score has a range of 0 to 52, with higher scores indicating better QoL.

6.4. Additional Details on Statistical Methods

6.4.1. SAS Code for ANCOVA Analysis

The primary analysis of the primary endpoint utilizes ANCOVA analysis for evaluating the percentage change from baseline to Week 26 in proteinuria. Sample code is provided below:

Step 1: Impute data on or after receipt of additional standard of care therapy (LN cohort only) using the value collected at the time of flare

Step 2: Impute data on or after treatment discontinuation using multiple imputation as described in Section 6.4.3.

Step 3: Analyze imputed datasets using ANCOVA analysis, including comparisons between the 180mg vs placebo and alxn2050 vs placebo:

```
proc mixed data = xxxx;

by shift _imputation_;

class trt01pn (ref = "3") stratavn;

model chg = trt01pn base stratavn/ solution;

lsmestimate trt01pn '120 mg' 1 0 0/cl alpha=0.05;

lsmestimate trt01pn '180 mg' 0 1 0/cl alpha=0.05;

lsmestimate trt01pn 'placebo' 0 0 1/cl alpha=0.05;

lsmestimate trt01pn '120 mg and 180 mg' 0.25 0.75 0/cl alpha=0.05;

estimate '180 mg vs placebo' trt01pn 0 1 -1/cl alpha=0.1;

estimate '120 mg and 180 mg vs placebo-dif weight' trt01pn 0.25 0.75 -1/cl alpha=0.1;

ods output Estimates=est_;

ods output LSMEstimates=estlsm_;

run;
```

where trt01pn is the randomized treatment group, base is the proteinuria value at baseline, strat is the randomization stratification variable, and chg is the change from baseline in log(proteinuria).

Step 4: Inferences from each complete data set will be combined to obtain an overall test statistic for each treatment effect.

```
proc mianalyze data=xxxx;
    by label;
    modeleffects estimate;
    stderr;
run;
```

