2. STATISTICAL HYPOTHESES

The primary hypothesis for this study is that ALXN2050 180 mg bid is superior to placebo in decreasing proteinuria. Hypothesis testing will be 1-sided and performed at the 0.05 level of significance for each disease cohort without adjusting for multiplicity.

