4.2.2. Main Analytical Approach

An analysis of covariance (ANCOVA) will be used for the primary efficacy analysis to compare reductions in proteinuria between the ALXN2050 180 mg bid treatment and placebo groups. The ANCOVA model will include change from baseline in log-transformed proteinuria as the response variable and will adjust for baseline log proteinuria and the randomization stratification factor. The treatment effect will be evaluated using the least-squares mean difference between treatment groups. The point estimate and 2-sided 90% CI for the mean difference of log-transformed proteinuria will be back transformed (via exponentiation) to obtain the geometric mean ratio (GMR) and corresponding 2-sided 90% CI. The values will then be expressed as percentage change in adjusted geometric mean of proteinuria at Week 26 relative to baseline.

The analysis will be performed for both proteinuria measures, UPCR and UP, in both cohorts even though the primary endpoint will be measured by UPCR for the LN cohort and by UP for the IgAN cohort.

The randomization stratification factor will be based on strata verified by laboratory and allowed concomitant therapy data from electronic case report form (eCRF). Sensitivity analysis may be performed using strata as randomized in the interactive response technology.

The data after the intercurrent events will be treated as missing, and all the missing data will be imputed according to the following assumptions:

In the LN cohort, only data up to the point of additional standard of care therapy will be included as observed for participants who receive additional standard of care therapy due to renal flare. Data on or after additional standard of care therapy for these participants is treated as missing regardless of whether the data is collected or not. The measurement performed at the time of renal flare (ie, proteinuria value from the 24-hour urine collection) will be carried forward to all subsequent visits.

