• In both the LN and IgAN cohorts, data occurring on or after treatment discontinuation will be treated as missing. It is assumed that study participants follow the behavior of their randomized arm. All the missing data will be imputed through multiple imputation (MI) under MAR assumption. Participants with missing data can be modeled based on similar participants with available data if relevant observed factors are accounted for in the model. This MI procedure can be performed in 3 steps: 1) Impute missing data (eg, use PROC MI, *m* times); 2) Analyze each of the *m* complete data sets (eg, use PROC ANCOVA); and 3) Combine results across *K* multiply imputed datasets using Rubin's rule (eg, PROC MIANALYZE).

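### The sample pooling code for the primary contrast omits the 90% level and the ANCOVA residual degrees of freedom, so at software defaults it prints a 95% interval beside a 1-sided 5% test (minor code-text correction)

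*SAP*

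**What the plan says.** SAP section 2 sets the test: "Hypothesis testing will be 1-sided and performed at the 0.05 level of significance for each disease cohort without adjusting for multiplicity". SAP 4.2.2 sets the interval: "The point estimate and 2-sided 90% CI for the mean difference of log-transformed proteinuria will be back transformed". Protocol 9.4.6.1 gives the same 90% level. The tipping-point analysis in SAP 4.2.3 uses a 2-sided p-value of 0.10 as its threshold, which agrees with both.

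For pooling, SAP 4.2.2 names Rubin's rule, with PROC MIANALYZE as an example. The only further detail is in SAP 6.4.1, introduced by "Sample code is provided below":

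- **Step 3** fits the ANCOVA in each imputed dataset and sets levels line by line. Arm means get `alpha=0.05`. The treatment contrasts get `alpha=0.1`, for example "estimate '180 mg vs placebo' trt01pn 0 1 -1/cl alpha=0.1".
- **Step 4** pools with "proc mianalyze data=xxxx", run by label, using the estimates and their standard errors. No level and no complete-data degrees of freedom are given. In the text as it reads here, no variable is named for the standard error.

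SAP 6.4.4 and 6.4.5 (placebo-based imputation and tipping point) refer back to 6.4.1 for the ANCOVA code. They name PROC MIANALYZE but print no call of their own.

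**The concern.** The `alpha=0.1` in Step 3 governs only the limits computed inside each imputed dataset. Step 4 does not read those limits. It rebuilds an interval from the pooled estimate and standard error, at whatever level the pooling call uses. With no level given, the procedure's default applies, taken here to be 95%. The primary GMR could then be reported with an interval that does not match the text. In a band of results that interval would include 1 although the 1-sided 5% test is met. Protocol 9.5 assigns the Week 26 analysis to dose selection and Phase 3 planning, where the interval is likely to be read closely.

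The second omission acts on the reference distribution. Without `edf=`, the complete-data degrees of freedom are taken as infinite, so the pooled t is close to a normal quantile even though the ANCOVA has only some 50 to 65 residual degrees of freedom.

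**Working it through.** **Inputs from the documents.** SD of log change 0.60; 10% dropout; 30 (LN) and 24 (IgAN) per main arm; cohort totals 70 and 56; design GMRs 0.40/0.60 = 0.667 (LN) and 0.55/0.85 = 0.647 (IgAN), all from SAP section 5. There are 1000 imputations (SAP 6.4.3). The ANCOVA has 5 parameters: intercept, two treatment contrasts, baseline and one stratum term.

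**Assumed.** Default level 0.05 and infinite complete-data df in PROC MIANALYZE. The fraction of missing information is not in the documents, so it is varied from 5% to 30%.

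**1. The plan's own pairing.** (1 - 0.90)/2 = 0.05. The stated interval and the stated test agree.

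**2. Standard errors and residual df.**
- LN: 0.6 × √(2/27) = 0.1633; df = 70 - 5 = 65.
- IgAN: 0.6 × √(2/21.6) = 0.1826; df = 56 - 5 = 51.

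As a check on the LN value, 0.4055/0.1633 - 1.645 = 0.838, which gives power 79.9%, matching the SAP's figure of about 80%.

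**3. Pooled df without `edf=`.** Rubin df = (m - 1)(1 + 1/r)². At 10% missing information r = 0.1/0.9, so df = 999 × 10² = 99,900. The 97.5% quantile is 1.960 and the 95% quantile is 1.645.

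**4. Width.** Ratio of half-widths, default call against 90% on the residual df:
- LN: 1.960/1.669 = 1.175.
- IgAN: 1.960/1.675 = 1.170.

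Split by cause, the default level contributes 1.960/1.645 = 1.19 (wider). Infinite df contribute 1.645/1.669 = 0.986 (LN) and 1.645/1.675 = 0.982 (IgAN), which is narrower. Using small-sample pooled df (about 57 and 44 at 10% missing information) gives 17.2% and 16.7%. Over 5-30% missing information the range is 16.0% to 17.3%.

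**5. Intervals at the design effects**, exp(log GMR ± critical value × SE):

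| Cohort | 90%, residual df | Default call |
|---|---|---|
| LN | 0.508-0.875 | 0.484-0.918 |
| IgAN | 0.477-0.879 | 0.452-0.925 |

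**6. Band where test and interval disagree**, from exp(-1.960 × SE) to exp(-1.645 × SE), using the p-value as coded:
- LN: 0.726 to 0.764.
- IgAN: 0.699 to 0.741.

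The chance of landing there at the design effect is Φ(1.96 - δ/SE) - Φ(1.645 - δ/SE), where δ is the size of the log GMR. With δ/SE = 2.483 (LN) and 2.384 (IgAN), this is about 10% and 11%.

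**7. Effect of the missing `edf=` on the test.** P(t with 65 df > 1.645) = 5.24% (LN) and P(t with 51 df > 1.645) = 5.31% (IgAN), against 5.0%. With small-sample pooled df at 10% missing information the values are 5.28% and 5.35%. At 30% they are 5.36% and 5.46%.

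**The case against.** The governing text is clear. Two documents give 90% for this contrast, and the code is a sample with a placeholder dataset name. Step 3 also runs by a shift variable that belongs to the tipping-point analysis, and it writes separate outputs for contrasts and arm means, so one pooling call cannot be the finished program. Table specifications sit in a separate Data Presentation Plan that is not available here. A careful programmer would carry the 90% level across. All of this stands, and it is why the point is minor.

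A reader might infer more than the documents support:

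- **That the plan specifies a 95% primary interval.** It does not. No section asks for one on this contrast, and the 95% level arises only if the call is run at defaults.
- **That the primary decision changes through the missing level.** It does not. The level option affects printed limits only, and the mismatch is in the conservative direction.
- **That infinite df widen the interval.** They narrow it by about 2%. All the widening comes from the level.
- **That the placebo-based and tipping-point code is itself wrong.** Those sections print no pooling call. They would be affected only by reusing this one.

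It can also be said that large-sample Rubin df are a legitimate reading of Rubin's rule and that a few tenths of a percentage point is negligible in Phase 2. The size is indeed small. But no text states the pooled df, so on this half the main text cannot correct the code.

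**Conclusion.** The gap between code and text is real. As printed, Step 4 cannot inherit the 90% level from Step 3, and nothing else in the SAP supplies the pooled df. Run at defaults, it yields a primary interval about 17% too wide on the log scale (about 19% from the level, less about 2% from infinite df), with a band of results where the test passes and the interval includes 1. Separately, the 1-sided level is about 5.2-5.3% on the residual df.

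This rests on the procedure's defaults, which the documents do not state, and on the planned SD, dropout and cohort sizes. SAP section 1 records that enrollment was paused. If the cohorts ended smaller than planned, the residual df would be lower and the effect of omitting `edf=` slightly larger. The severity is a minor code-text correction: the pooled estimate and standard error are untouched, and the p-value is touched only slightly, through the df.

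**What to change.** In SAP 6.4.1 Step 4:

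1. For the treatment contrasts, add `alpha=0.1` and `edf=` set to the residual df of the fitted ANCOVA (65 and 51 at the planned sizes; use the actual values at analysis).
2. Pool the arm means in a separate call with `alpha=0.05`, so that each set keeps the level Step 3 gives it.
3. Name the variable holding the standard error.
4. State that the 1-sided p-value is taken from the pooled t statistic and its df, in the direction favoring ALXN2050.
5. Use the same contrast call where 6.4.4 and 6.4.5 refer back to 6.4.1.

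The cost is two options, one extra call and a sentence of text, with no change to data, design or sample size. It should be done before the primary analysis is run.

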6.4.2. SAS Code for MMRM Analysis

The secondary endpoint of percentage change from baseline to Week 50 in proteinuria utilizes MMRM analysis. Other secondary endpoints assessing longitudinal changes will also utilize MMRM analysis. Sample code is provided below:

Step 1: Impute data on or after receipt of additional standard of care therapy (LN cohort only) using the value collected at the time of flare or suboptimal response, if applicable

Step 2: Analyze imputed dataset using MMRM analysis-adjust the least square mean estimate based on number of scheduled visit for each of the endpoint/relevant analysis.

where subjid is the participant identifier variable, trt01pn is the randomized treatment group, avisitn is the visit variable, base is the proteinuria value at baseline, strat is the randomization stratification variable, and chg is the change from baseline in log(proteinuria).

6.4.3. SAS Code for Multiple Imputation

For the primary analysis of the primary endpoint, responses after treatment discontinuation will be imputed using a multiple imputation approach assuming the data are MAR and using a regression model. Sample code is provided below:

Step 1: Imputation using a monotone regression model at Week X

```
proc mi data=ADEFF out=outmi seed=123 nimpute=1000;
class trt01pn strat;
var trt01pn base strat Week26;
monotone reg(/details);
run;
```

where trt01pn is the randomized treatment group, base is the proteinuria value at baseline, strat is the randomization stratification variable, and Week26 is the change from baseline in log(proteinuria) at Week 26.

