Sensitivity analysis due to dosing pause- excluding data points impacted by dosing pause	LN and IgAN cohorts	Dosing pause will be regarded as an intercurrent event, in which the analysis is similar to that of treatment discontinuation.	
Sensitivity analysis due to dosing pause- excluding participants impacted by dosing pause	LN and IgAN cohorts	The participants in the population of no impact by dosing pause will be included.	

Abbreviations: IgAN = immunoglobulin A nephropathy; LN = lupus nephritis

Further details of these sensitivity analyses are below.

- Placebo-based multiple imputation + carry-forward: The primary endpoint will be analyzed in the same manner as the primary analysis, except that data collected on or after treatment discontinuation will be assumed missing and imputed using placebobased multiple imputation where it will be assumed that outcomes occurring after treatment discontinuation will follow the trajectory of outcomes similar to the one in the placebo treatment group, taking into account observed values prior to treatment discontinuation (Ratitch, 2014).
- Placebo-based multiple imputation: The primary endpoint will be analyzed in the same manner as the primary analysis, except data collected on or after treatment discontinuation or receipt of additional standard of care therapy (LN cohort only) will be assumed missing and imputed using placebo-based multiple imputation.
- Tipping point analysis: An additional sensitivity analysis will be performed based on the delta-adjusted stress testing method (tipping point analysis). This approach assumes that participants who discontinue from ALXN2050 treatment or who receive additional standard-of-care therapy (for the LN cohort only) experience worsening, defined by a prespecified adjustment (delta) in the primary efficacy endpoint compared with the observed efficacy score of participants who continue the study to the next visit. For each value of delta, the treatment effect will be determined, and the value of delta for which the nominal 2-sided p-value crosses 0.10 will be considered

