6.1.6. Analysis Value

The values being considered for analysis at a specific post-Baseline time point will be based on the analysis visit assigned to that value. If there is more than 1 nonmissing value for a specific assessment with the same analysis visit, the value used for analysis will be the one for which the calculated number of days from baseline is closest to the scheduled visit day. If 2 values have the same analysis visit and are the same distance away from the scheduled visit day, the earlier of the 2 values will be used for analysis.

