6.4.4. SAS Code for Placebo-Based Imputation

A sensitivity analysis for the primary endpoint will be performed using placebo-based imputation for responses after treatment discontinuation. In this analysis, data occurring after treatment discontinuation will be set to missing and multiple imputation will then be performed using a regression method obtained only from placebo-treated participants with terms for baseline value and the randomization stratification variable.

The following is a partial SAS code for the placebo-based pattern imputation at Week 26:

```
proc mi data=ADEFF out=outmi seed=123 nimpute=1000; class trt01pn strat; var base strat Week26; monotone reg(/details); mnar model (Week26/modelobs=(trt01pn='Placebo')); run;
```

where trt01pn is the randomized treatment group, base is the proteinuria value at baseline, strat is the randomization stratification variable, and Week26 is the change from baseline in log(proteinuria) at Week 26.

The 1000 imputed data sets are then analyzed using ANCOVA (refer to Section 6.4.1 for SAS code) and PROC MIANALYZE procedure will be used to generate valid statistical inferences about these parameters.

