6.4.5. SAS Code for Tipping Point Analysis

A sensitivity analysis for the primary endpoint will be performed using the tipping point approach where a search is conducted for a tipping point that reverses the study conclusion from being favorable to ALXN2050 to being unfavorable. For the tipping point sensitivity analysis, the missing data mechanism for the missing change from baseline in log proteinuria values at Week 26 will be considered to be missing not at random (MNAR). Imputations are performed for missing change observations for ALXN2050 treated participants assuming not the full treatment effect, but the treatment effect adjusted by a shift parameter delta. After obtaining complete data sets for multiple shift parameters, the complete data sets will be used in the MMRM analysis, and inferences from each complete dataset will be combined using SAS PROC MIANALYZE to obtain an overall test statistic for each shift value. Multiple shift parameters will be tested until the inference concludes that statistical significance disappears.

The following is a partial SAS code for the multiple imputation analysis for a specified shift parameter at Week 26:

```
proc mi data=ADEFF out=outmi seed=123 nimpute=1000;
class trt01pn strat;
monotone method=reg;
var trt01pn strat base Week26;
mnar adjust (Week 26 /shift=delta adjustobs=(trt01pn='ALXN2050'));
```

where trt01pn is the randomized treatment group, base is the proteinuria value at baseline, Week26 is the change from baseline in log(proteinuria), and strat is the randomization stratification.

The 1000 imputed data sets are then analyzed using ANCOVA (refer to Section 6.4.1 for SAS code) and PROC MIANALYZE procedure will be used to generate valid statistical inferences about these parameters.

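### The primary imputation uses only the ANCOVA's own terms and ignores on-treatment response; SAP 4.2.3 and 6.4.4 describe the placebo-based imputation differently

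*SAP*

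**What the plan says.** **Primary imputation.** SAP 4.2.2 sets data on or after treatment discontinuation to missing in both cohorts and imputes them under MAR: "It is assumed that study participants follow the behavior of their randomized arm". It makes this conditional on the model containing the relevant observed factors, but names none. The code in 6.4.3 is "var trt01pn base strat Week26". The ANCOVA in 6.4.1 is "model chg = trt01pn base stratavn/ solution". In LN, values after additional standard of care therapy for renal flare are handled separately: "Data on or after additional standard of care therapy for these participants is treated as missing", and the 24-hour value at the flare is carried forward.

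**Placebo-based imputation.** SAP 4.2.3 says outcomes after discontinuation "will follow the trajectory of outcomes similar to the one in the placebo treatment group, taking into account observed values prior to treatment discontinuation". SAP 6.4.4 fits the model on placebo participants "with terms for baseline value and the randomization stratification variable", and its code agrees with that.

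**Tipping point.** SAP 6.4.5 starts from the same predictors: "var trt01pn strat base Week26".

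**Data not used.** Spot UPCR is scheduled at Weeks 2, 4, 8, 12, 16 and 20 in LN and Weeks 2, 6, 12 and 18 in IgAN (Protocol 1.3), with two consecutive samples at Week 16 (LN) and Week 18 (IgAN) (Protocol 8.1.2). SAP 4.3.1.1 already gives spot UPCR its own MMRM.

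**Labelling.** The code sections define `base` as baseline proteinuria, whereas 4.2.2 requires log baseline.

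**The concern.** When an imputation model contains exactly the analysis model's terms, it adds no information to an analysis of the available data. MAR must then hold given arm, baseline and stratum alone. Two participants on the same arm with the same baseline receive the same imputation distribution even if one was responding at Week 18 and the other was not.

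If poor responders leave active treatment more often than placebo, the estimate is too favourable. If they leave placebo more often, it is too conservative. Protocol 7.2 lists lack of efficacy as a reason for withdrawal, so response-related stopping is plausible. A difference between arms is an assumption, since SAP 5 plans a single 10% rate.

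The conflict between 4.2.3 and 6.4.4 needs no dropout assumption: the plan supports two different programs for one sensitivity analysis.

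**Working it through.** **1. Planning values.** For LN, SAP 5 gives log(0.60) - log(0.40) = 0.4055 with SD 0.60. With 30 x 0.9 = 27 evaluable per arm, SE = 0.60 x sqrt(2/27) = 0.163. Then 0.4055/0.163 - 1.645 = 0.84, and power is 0.799, matching the stated 80%. For IgAN the true difference is log(0.55) - log(0.85) = -0.4353, a GMR of 0.647, with 24 per arm plus 8 on 120 mg.

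**2. The imputation equals the available-data ANCOVA.** With proper regression imputation and Rubin's rules, the 6.4.3 model matched that ANCOVA within 0.005 on the log scale in each of six trial-size data sets. One LN example gave -0.4075 (SE 0.165) against -0.4068 (SE 0.163). Over the simulated IgAN trials the mean difference was at most 0.0003.

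**3. Bias by hand.** Assumed, not in the documents: correlation rho = 0.7 between late log spot UPCR change and Week 26 log change, and dropout logistic in the spot response with slope 2 per SD (odds ratio 7.4). In an arm with dropout p, the available-data mean is shifted by

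-rho x SD x [p/(1-p)] x E(Z | dropout),

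where Z is the standardised spot response. Numerical integration gives E(Z | dropout) = 1.284 at p = 0.10 and 1.655 at p = 0.02.

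- Active, 10%: 0.7 x 0.60 x 0.1111 x 1.284 = 0.0599
- Placebo, 2%: 0.7 x 0.60 x 0.0204 x 1.655 = 0.0142
- Net shift: -(0.0599 - 0.0142) = -0.0457; GMR = exp(-0.4353 - 0.0457) = 0.618
- The mirror pattern gives exp(-0.4353 + 0.0457) = 0.677; equal dropout cancels.

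SE = 0.60 x sqrt(1/21.6 + 1/23.52) = 0.179, so the shift is 0.26 SE. Under the null this implies a one-sided error of about Phi(-1.645 + 0.256) = 8.2%.

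**4. Simulation, IgAN primary GMR (truth 0.647).** The ranges cover correlations of 0.5, 0.7 and 0.8. Slopes 1, 2 and 4 are odds ratios of 2.7, 7.4 and 55.

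| Dropout active/placebo | Slope 1, coded | Slope 2, coded | Slope 4, coded | Spot UPCR added (all slopes) |
|---|---|---|---|---|
| 10%/2% | 0.627-0.634 | 0.613-0.626 | 0.609-0.620 | 0.646-0.650 |
| 2%/10% | 0.661-0.673 | 0.671-0.682 | 0.672-0.692 | 0.643-0.650 |

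At correlation 0.7 and slope 2:
- 10%/5% gives 0.629 coded and 0.646 with spot; 5%/10% gives 0.664 and 0.646.
- 10% response-driven in both arms gives 0.645 with either model.
- A simplified two-arm run (20,000 trials per scenario) gave 0.618 and 0.647 for 10%/2%, and 0.678 and 0.648 for the mirror.
- One-sided type I error, coded versus spot: 7.8% and 5.0% (10%/2%), 2.7% and 4.6% (mirror), 5.1% and 5.0% (symmetric).

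**5. Noisy spot samples.** If dropout follows the underlying level rather than the measured sample (assumed single-sample correlation 0.6, reliability 0.7), 10%/2% gives 0.617 coded, 0.637 with one sample and 0.641 with the mean of two. The log biases are -0.047, -0.016 and -0.009, so one sample removes about two thirds of the bias and two remove about 80%.

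**6. Placebo-based GMR under its two descriptions** (correlation 0.7).

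| Dropout | As 6.4.4 | With spot values, as 4.2.3 |
|---|---|---|
| Random, 10% both arms | 0.675 | 0.659 |
| 10%/2%, slope 2 | 0.648 | 0.659 |
| 2%/10%, slope 2 | 0.683 | 0.649 |

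**7. LN** (30/30 plus 10; assumed flares 15% placebo, 10% on 120 mg, 5% on 180 mg; slope 2; Weeks 16 and 20 as predictors). Bias in log GMR as coded: -0.042 (10%/2%), +0.027 (mirror), -0.006 (symmetric). With spot UPCR: -0.006, 0.000, -0.002. Every simulated LN trial had a non-monotone missing-data pattern.

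**The case against.** **A valid choice, and sample code.** The model fits the stated assumption that participants follow their randomized arm, and the code is labelled sample or partial. That stands: this is a weakness, not an error. But no other section lists the predictors, and 6.4.4 restricts them in prose as well as in code.

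**No 24-hour collection falls between Screening and Week 26,** apart from LN flare visits. Baseline is then usually the only earlier endpoint value, and 4.2.3 could be read as satisfied. This narrow reading is possible, but one baseline value is not a trajectory. Spot UPCR is a different measure, especially for IgAN in g/day, and the correlation is assumed; an auxiliary predictor only needs to correlate with the endpoint.

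**Blinding.** Sites are blinded to Week 50 (Protocol 6.3.2), so a single response-based rule should act in both arms. Under such a rule (10% overall, spot effect assumed to be 80% of the Week 26 effect) there is no bias under the null. Under the planned effect the GMR is 0.655-0.689, always conservative. This is the strongest point, and it makes inflated type I error the less likely direction. It does not remove the problem: a simulation under that rule gave 0.670 as coded, with power 71% versus 77% with spot UPCR.

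**Sensitivity analyses.** The treatment-policy, tipping-point and placebo-based analyses cover part of this. The tipping-point shift can reach any delta. Treatment policy answers a different question, and the placebo-based result depends on which description is programmed.

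**Conclusion.** The concern holds, as an improvement that should be made rather than a fatal flaw. Three facts rest on the text alone: the primary imputation repeats the ANCOVA's terms, no post-baseline value enters it, and the two descriptions of the placebo-based imputation do not match. The dosing-pause sensitivity analysis that treats the pause like discontinuation inherits the same model.

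The size rests on assumptions. Under differential, response-driven dropout the shift is about 0.1 to 0.4 of an SE of about 0.18, from roughly 2.4 versus 0.5 discontinued participants in the 10%/2% case. Under symmetric dropout there is no material bias. Confidence in the magnitude is medium, because neither the correlation nor the dropout pattern is in the documents.

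**What to change.** 1. In SAP 4.2.2 and 6.4.3, add pre-discontinuation log spot UPCR at one or two late visits (Weeks 16 and 20 for LN, Weeks 12 and 18 for IgAN) beside treatment, log baseline and stratum. Fill intermittent gaps first with an FCS or MCMC step, because the monotone regression needs a monotone pattern.
2. Use the same predictors in 6.4.4, so that it matches 4.2.3, and in 6.4.5. In 6.4.4, apply the placebo-reference rule to post-discontinuation spot values as well as to Week 26.
3. Use the single spot value chosen under 6.1.6, where "the value used for analysis will be the one for which the calculated number of days from baseline is closest" to the scheduled day. If the two consecutive Week 16 or 18 samples are averaged instead, state this as an exception.
4. For LN, set spot values on or after additional standard of care therapy or discontinuation to missing before imputation, and leave the flare carry-forward of Week 26 unchanged. This is for consistency with 4.2.2 and has little numerical effect.
5. Define `base` as log baseline proteinuria.

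The cost is SAP wording and a few lines of code, on data already collected. The statistical price is one or two more imputation parameters in small arms:
- Primary model: the SE moves between -2.7% (0.1878 to 0.1827, random dropout) and about +4% (0.1759 to 0.1828 with one predictor or 0.1833 with two; symmetric dropout, slope 4).
- Placebo-only model, fitted on about 22-24 IgAN participants: the SE moves between -3.5% (0.1921 to 0.1853) and +5.8% (0.1802 to 0.1907 with two predictors). Its between-trial SD rises by up to 11% (0.1604 to 0.1778).
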